### 5.4.3 Interim Analysis

An interim analysis for futility will be conducted by an independent statistician. The purpose of the interim analysis is to help make a decision whether to continue the trial to the planned sample size, or to stop the trial for futility. No increase or decrease to the sample size will be performed, except to stop the trial for futility, therefore no adjustment to type-1 error is indicated. The interim analysis will be based on conditional power analysis when approximately 60 subjects (per group) have completed the study. Only absolute lesion reduction count and IGA data (2 point reduction, and Clear or Almost Clear (0, 1)) will be analyzed following the same statistical approaches as pre-specified in the Efficacy Analysis section.

Conditional power for differences in proportions will be calculated using a Normal approximation, two-sided alpha of 0.05, assuming future data will follow the current trend. The decision rules and algorithm for interim analysis are shown in Figure 1:

Figure 1  
 Graphical Illustration of Interim Analysis Algorithm  
 N=120 (N=60 per group)

The independent unblinded statistician will receive the interim study data and the randomization information confidentially from the CRO. The independent statistician will then follow the algorithm above and make a recommendation accordingly. This

recommendation will be reviewed by designated sponsor's representatives who will make the final decision as to continue the trial as planned or stop for futility. Upon receiving the recommendation, the sponsor may ask the independent statistician to examine additional data before the final decision is made. All communications between the unblinded statistician and the sponsor's representatives will be kept confidential and unknown to all personnel involved in the trial (other sponsor's personnel, CRO, and clinical center personnel). A charter will be written to describe in detail the process and roles related to this interim analysis. This charter will name the independent statistician to conduct the interim analysis, and the sponsor's designated personnel that will make final decisions.

#### **5.4.4 Safety Analysis**

Adverse events will be categorized by system organ class and Preferred Term from the current version of MedDRA. Treatment-emergent adverse events will be summarized overall and by seriousness, by severity, and by relationship to treatment using frequencies and percentages. Adverse events will be considered treatment-emergent if the onset date is on or after the first dose of study medication.

Changes from baseline in vital signs and laboratory parameters, and shifts from baseline laboratory parameters will be summarized by treatment.

Safety summaries will be presented for the double-blind study period. Additional summaries will be presented for the 4 week follow-up study period, based on the treatment received during the double-blind study period.

#### **5.4.5 Week 16 (4 Week Follow-Up) Summary**

Summary statistics for Week 16 study period will include baseline demographics, disposition, exposure, safety, and efficacy variables.

Efficacy summaries will include:

- The absolute change from baseline to Week 16 in inflammatory lesions (papules and pustules).
- IGA at Weeks 16: 2 point reduction; Clear or Almost Clear (IGA 0, 1).
- Percentage of subjects with an Investigator Assessment of Erythema (IAE) of clear or almost clear (0 or 1) at Week 16.
- Percentage of subjects with telangiectasia score of none or mild (0 or 1) at Week 16.
- Percentage of subjects with scaling/peeling score of none or mild (0 or 1) at Week 16.
- Percentage of subjects with pruritus score of none or mild (0 or 1) at Week 16.

Safety summaries will include:

- concomitant medications
- adverse events that were emergent during the follow-up study period
- vital signs and laboratory tests.

All Week 16 summaries will be performed by original double-blind randomized treatment group, and overall.

#### **5.4.6 Compliance (Study Product Utilization and Exposure)**

The total number of days product was applied during the double-blind study period from the study medication diary will be summarized by treatment. Per day product usage will be estimated for each dispensing interval and overall as the weight of product used divided by the number of days product was applied. The total number of days product was applied and the per day product usage will be summarized by N, mean, standard deviation, median, minimum, and maximum.

### **6.0 Data Handling Conventions**

This section contains the data handling conventions that will be used to carry out the statistical analyses.

#### **6.1 Baseline and Follow-Up Visits**

Visits and timepoints (Baseline; Interim visits [Weeks 1, 3, 6, 9], final double-blind visit [Week 12], and Follow-up visit: [Week 16]) for all analyses will be as record on the eCRFs, except as noted below. Baseline will be the later of the non-missing values from the Screening and Baseline/Day 1 visits scheduled to occur prior to receiving study medication. Unscheduled visits will not be used in for any analyses but will be included on data listings.

If a subject does not complete the study, the final double-blind visit (Week 12) will be reassigned to a scheduled visit based on the relative day ranges in the following table. If a result already exists for the calculated visit or the calculated visit was not a scheduled visit, the next scheduled visit will be assigned.

Study Day Range	Calculated Visit
$2 \leq \text{Study Day} \leq 15$	Week 1
$16 \leq \text{Study Day} \leq 32$	Week 3
$33 \leq \text{Study Day} \leq 53$	Week 6
$54 \leq \text{Study Day} \leq 74$	Week 9
$\text{Study Day} \geq 75$	Week 12

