7.2.3 Withdrawal from Study Criteria

Reasons for discontinuation of study medication include, but are not limited to, the following:

- Adverse Event
- Pregnancy
- Withdrawal By Subject
- Lost To Follow-Up. The Investigator will try to reach the subject, twice by telephone (document telephone calls) and once by certified letter, before considering the subject lost-to-follow-up. The lost to follow-up discontinuation will be reported on the appropriate eCRF, and a copy of the follow-up letter will be maintained in the Investigator's file.
- Study Terminated By Sponsor
- Physician Decision
- Non-Compliance with Study
- Other

CONFIDENTIAL

Version Date: 10 July 2015

All premature discontinuations from the study must be documented by the Investigator on the eCRF, and if due to an adverse event, on the Adverse Event Case Report page of the eCRF. All subjects should attempt to complete all visits and evaluations.

Subjects not completing the entire study should be fully evaluated (i.e., final double-blind Week 12 visit procedures performed during the double-blind period and the Follow-up Week 16 visit procedures during the follow-up period). All subjects are free to withdraw from participating in this study at any time and for whatever reason, specified or unspecified, and without prejudice to his or her medical care by a physician. Subjects who withdrawal from the study will not be replaced.

CONFIDENTIAL

Version Date: 10 July 2015

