7.3.2 Study Procedures by Visit

Visits following the Baseline Visit are to occur at the end of Weeks 1, 3, 6, 9, and 12 (Final Treatment Visit) and a follow up visit at Week 16. However, all interim study visits and the follow up Week 16 study visit may be conducted (on an individual subject basis) up to 3 days before or after the regularly scheduled study visit. An unscheduled visit may occur in the event that the investigator determines that the subject should be seen for safety or any other reasons.

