### **5.1 Sample Size Determination**

The primary objective of the study is to show superiority of Omiganan [REDACTED] over vehicle for the treatment of rosacea in patients with severe papulopustular rosacea (IGA Grade 4 with baseline inflammatory lesion count  $\geq 30$ ). A sample size calculation was made for two co-primary endpoints. For change from baseline in inflammatory lesions, it is assumed that in the Omiganan [REDACTED] treatment arm, subjects will have an average reduction of 13.5 inflammatory lesions, compared to 4 in the vehicle arm. The standard deviation is assumed to be 12. For 95% power, a sample size of 86 subjects (43 per group) is needed. For Investigator Global Assessment (IGA), it is assumed that Clear or Almost Clear (IGA of 0 or 1) at Week 12 has a lesser power than 2 point reduction. It is also assumed that 17% of the subjects in the Omiganan [REDACTED] treatment arm versus 6% in the vehicle arm will have IGA of clear or almost clear at Week 12. For 95% power and using a Fisher's Exact test, 450 subjects (225 in each arm) are needed. Therefore, the number of subjects needed to ensure at least 95% power for both endpoints is 450.

The sample sizes were calculated using 95% power in order to ensure 90% power across two Phase 3 studies.

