### 5.4.2 Efficacy Analysis

The co-primary endpoint of absolute change from baseline in inflammatory lesions will be analyzed using an Analysis of Covariance (ANCOVA) model, with treatment as a main effect, and pooled center as a covariate. To investigate consistency of efficacy results across study centers, treatment by center interaction will be tested at 0.1 level of significance and, if significant, it will be further be explored.

No adjustments will be made for multiple comparisons of efficacy endpoints. All analyses will be considered exploratory in nature due to the discontinuation of enrollment following the interim analysis.

Both IGA endpoints will be analyzed using a Cochran–Mantel–Haenszel (CMH) test, with center as the stratification factor. If the overall IGA response rates are less than 10%, a Fisher’s Exact test will be used to corroborate the CMH test. All tests of the co-primary endpoints will be analyzed.

For all efficacy analyses, small centers may be pooled in order to ensure sufficient cell counts for statistical testing.

Subgroup summaries (e.g. Gender, Age, Race, and Center) of the co-primary endpoints will be performed

[figure not shown]

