#### **6.2 Missing Data**

The primary method of dealing with missing data is multiple imputation (MI) technique. All co-primary and secondary endpoints will be analyzed using MI for missing data. As a sensitivity analysis, Observed Case and Baseline Observation Carried Forward (BOCF) will be utilized for the co-primary endpoints only.

The MI technique will be implemented as follows:

a) 100 imputed datasets will be generated to impute missing data using the below SAS code.

1) For inflammatory lesions

```
Proc MI NIMPUTE=100 SEED=20170307  
MIN = . 0 0 0 0 0 0  
MAX = . . . . . . .  
ROUND = . 1 1 1 1 1 1;  
class sex;  
var sex base w1 w3 w6 w9 w12;  
fcs reg(w1) reg(w3) reg(w6) reg(w9) reg(w12);  
run;
```

2) For IGA

```
Proc MI NIMPUTE=100 SEED=20170307  
MIN = . 0 0 0 0 0  
MAX = . 4 4 4 4 4  
ROUND = . 1 1 1 1 1;  
class sex;  
var sex w1 w3 w6 w9 w12;  
fcs reg(w1) reg(w3) reg(w6) reg(w9) reg(w12);  
run;
```

b) The 100 imputed datasets will each be analyzed separately by the methods described in Section 5.4.2.

1) For inflammatory lesions, individual LS means and associated standard errors as well as estimates and standard errors from the pairwise comparison of treatments from the analysis of each imputation will be combined into single estimates, standard errors, and p-value using PROC MIANALYZE as displayed below.

```
Proc MIANALYZE;  
Modeleffects estimate;  
Stderr stderr;  
run;
```

The p-value for the treatment by center interaction will be based on the average of p-values from each the analyses of each imputation.

- 2) For IGA, estimates of the event rates will be based on the average of rates from each imputation. The CMH test statistic from the analysis of each imputation will be converted to a Normal Z score by taking the square root and adjusting for direction (change to a negative value if Omiganan group is worse than Vehicle). These Z scores (with SE=1) will be combined into a single p-value using PROC MIANALYZE as displayed below:

```
Proc MIANALYZE;  
Model effects estimate;  
Stderr SE;  
run;
```

Similarly, the p-values for the one-sided Fisher's Exact test of each imputation will be converted to a Normal Z score using the inverse normal function. These Z scores (with SE=1) will be combined into a single p-value using the same PROC MIANALYZE code.

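### Does counting an exit soon after Week 9 as the Week 12 result leave those dropouts untested by the sensitivity analyses?

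*SAP*

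**What the plan says.** Protocol 7.2.3 asks for an exit assessment: "Subjects not completing the entire study should be fully evaluated (i.e., final double-blind Week 12 visit procedures performed during the double-blind period". SAP 6.1 takes visits as the eCRF records them, so without a further rule an exit at any time could carry the Week 12 label. The SAP prevents most of this: "If a subject does not complete the study, the final double-blind visit (Week 12) will be reassigned to a scheduled visit", using day ranges in which Days 54-74 are Week 9 and Day 75 onward is Week 12. The tie-break follows: "If a result already exists for the calculated visit or the calculated visit was not a scheduled visit, the next scheduled visit will be assigned".

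SAP 6.2 makes multiple imputation (MI) the primary handling of missing values and adds: "As a sensitivity analysis, Observed Case and Baseline Observation Carried Forward (BOCF) will be utilized for the co-primary endpoints only". The imputation model for lesions lists "var sex base w1 w3 w6 w9 w12", so treatment is not in it. Protocol 7.3.2 lets interim visits vary: they "may be conducted (on an individual subject basis) up to 3 days before or after the regularly scheduled study visit". The schedule in Protocol 7.3.1 gives Week 12 the same 3-day tolerance. On status, SAP 5.4.2 states: "All analyses will be considered exploratory in nature due to the discontinuation of enrollment following the interim analysis".

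**The concern.** The day table puts Day 66, for example, in Week 9. If Week 9 was recorded on Day 64, the tie-break moves the Day 66 exit into Week 12, 19 days before the target day. The SAP's own table would not call that day Week 12.

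The value then counts as present. MI does not impute it, Observed Case keeps it and BOCF does not overwrite it. These subjects are dropouts, yet all three analyses of the co-primary endpoints use one identical number for them. If many subjects left in this interval, or if the arms differed in how many did, agreement between the primary and sensitivity analyses would be partly built in, and a reader could take it as more reassurance than it gives.

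**Working it through.** **1. The SAP's day ranges.** Visits fall at the end of Weeks 1, 3, 6, 9 and 12 (Protocol 7.3.2). With first dose on Day 1, the target day is 7 × week + 1: Days 8, 22, 43, 64 and 85. The midpoints are 15, 32.5, 53.5 and 74.5, which are the cut-points in SAP 6.1. The Week 12 window opens on Day 85 − 3 = Day 82.

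**2. Exit days rolled into Week 12.** These run from the day after the Week 9 visit to Day 74.

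| Week 9 visit | Exit days rolled | Number of days | Days before Day 85 | Mean |
|---|---|---|---|---|
| Day 61 (−3) | 62-74 | 13 | 11-23 | 17 |
| Day 64 (on time) | 65-74 | 10 | 11-20 | 15.5 |
| Day 67 (+3) | 68-74 | 7 | 11-17 | 14 |

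An exit visit that itself supplies the Week 9 result stays at Week 9. An exit by Day 74 with no Week 9 result on record does not reach Week 12.

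**3. How many subjects.** Assumed, since the documents give no dropout rate: 5-15% dropout, spread evenly over 84 days, everyone attending an exit visit. Share = dropout × days/84.

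- On time: 0.05 × 10/84 = 0.60% to 0.15 × 10/84 = 1.79%. That is 1.3-4.0 subjects per planned arm of 225, or 0.4-1.1 per arm of 60. The final sample size is not stated.
- Week 9 on Day 61: 0.77-2.32%.

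**4. Size of the timing error.** From SAP 5.1: lesion reductions of 13.5 and 4 (difference 9.5), and "The standard deviation is assumed to be 12". The sample sizes there reproduce: 43 per group gives 95.2% power by t-test, and 225 per arm gives 95.1% by Fisher's exact test for 17% against 6%. Assume the difference builds linearly to 9.5 at Day 85. Shift = 9.5 × share × mean days early/84.

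- On time: 9.5 × 0.0060 × 15.5/84 = 0.010, up to 9.5 × 0.0179 × 15.5/84 = 0.031 lesions.
- Day 61 with 15% dropout: 9.5 × 0.0232 × 17/84 = 0.045 lesions.
- Standard error = 12 × √(2/225) = 1.13, and 0.045/1.13 = 4%. At 60 per arm it is 12 × √(2/60) = 2.19.
- Clear or almost clear: 11 × share × mean days early/84 = 0.01-0.04 percentage points, or 0.05 with Day 61 and 15% dropout. The standard error is √((0.17 × 0.83 + 0.06 × 0.94)/225) = 2.96 points.

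The shift is proportional to dropout. At 30%, with Week 9 on Day 61, it is 2 × 0.045 = 0.09 lesions, or 8% of one standard error.

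**5. Effect of treating these values as missing in the sensitivity analyses.** In BOCF each would be set to no change. Fall in the lesion difference = 9.5 × share × (1 − mean days early/84).

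- On time: 0.046-0.138. Day 61 with 15% dropout: 0.176, and 0.176/1.13 = 16% of one standard error.
- Ratio to the timing error, on time: (84 − 15.5)/15.5 = 68.5/15.5 = 4.4.
- The Observed Case standard error would rise by the factor 1/√(1 − share): 0.3-0.9%, or 1.2% with Day 61 and 15% dropout.

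**6. Effect of imputing instead in the primary analysis.** On the linear course the measured exit values (mean of Days 65-74) carry a difference of 9.5 × 68.5/84 = 7.7. Now regress Week 12 on baseline to Week 9 without treatment, with SD 12, an assumed correlation of 0.6-0.9 between values three weeks apart (decaying with distance), and the two arms pooled. The imputed difference is 4.7-6.9. If benefit plateaus instead (28-day time constant), the figures are 9.1 measured and 6.0-8.5 imputed. Against the planned 9.5, the measured value is nearer in both cases.

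**The case for a change.** The best argument for a change is that it is cheap: two SAP sentences, one flag and one count by arm. Observed Case and BOCF are the only checks on missing data, and a check that uses the primary analysis's own value for some dropouts cannot show whether those dropouts matter. As a description of the rule, that stands.

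The proposed cure is weaker. It would replace a count taken 11-20 days early with one from baseline, about 84 days early, and it would remove observed values from an analysis named Observed Case. A cut at Day 75 would not close the gap either. A non-completer seen on Days 75-81 is also before the Day 82 window, is also labelled Week 12 and is also left alone by all three analyses. On the even-spread assumption that is 7 of 84 exit days, against 10 of 84 for the group the cut would catch. An exit on Day 74 would become missing while one on Day 75 would be kept.

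Nor can the error be called conservative. The linear course implies a slightly smaller difference than at Day 85, but these subjects have left the double-blind period. The protocol adds a 4-week follow-up to look for relapse, and if benefit wanes off drug an early value could overstate the Day 85 difference.

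What remains is a point of reporting: the study report could give, by arm, the number of non-completers' exit values labelled Week 12 from before Day 82. That needs no change to the plan and alters no result.

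**Conclusion.** The rule works as described, and no change is needed. SAP 6.1 is a pre-specified windowing convention that takes most early exits back out of Week 12. What it leaves there is a small group with real, late measurements. Observed Case and BOCF address missing values, so leaving a measured value in place is how they are meant to work. The error is one of timing and labelling.

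Under 5-15% evenly spread dropout, full attendance at exit visits and a linear course, the shift is 0.01-0.045 lesions, at most 4% of one standard error at 225 per arm, and at most about 0.05 percentage points on clear or almost clear. The dropout range is an assumption and not a bound; 30% dropout would double the largest lesion figure to 0.09. The direction is not determinable from the documents. Subjects lost without an exit visit remain missing and are covered by all three methods. With enrollment stopped and every analysis exploratory, no confirmatory conclusion depends on this, and the available remedy would move BOCF further than the error it addresses. Keeping the rule is a fair trade-off.

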#### **6.2 Missing Data**

The primary method of dealing with missing data is multiple imputation (MI) technique. All co-primary and secondary endpoints will be analyzed using MI for missing data. As a sensitivity analysis, Observed Case and Baseline Observation Carried Forward (BOCF) will be utilized for the co-primary endpoints only.

The MI technique will be implemented as follows:

a) 100 imputed datasets will be generated to impute missing data using the below SAS code.

1) For inflammatory lesions

```
Proc MI NIMPUTE=100 SEED=20170307  
MIN = . 0 0 0 0 0 0  
MAX = . . . . . . .  
ROUND = . 1 1 1 1 1 1;  
class sex;  
var sex base w1 w3 w6 w9 w12;  
fcs reg(w1) reg(w3) reg(w6) reg(w9) reg(w12);  
run;
```

2) For IGA

```
Proc MI NIMPUTE=100 SEED=20170307  
MIN = . 0 0 0 0 0  
MAX = . 4 4 4 4 4  
ROUND = . 1 1 1 1 1;  
class sex;  
var sex w1 w3 w6 w9 w12;  
fcs reg(w1) reg(w3) reg(w6) reg(w9) reg(w12);  
run;
```

b) The 100 imputed datasets will each be analyzed separately by the methods described in Section 5.4.2.

1) For inflammatory lesions, individual LS means and associated standard errors as well as estimates and standard errors from the pairwise comparison of treatments from the analysis of each imputation will be combined into single estimates, standard errors, and p-value using PROC MIANALYZE as displayed below.

```
Proc MIANALYZE;  
Modeleffects estimate;  
Stderr stderr;  
run;
```

The p-value for the treatment by center interaction will be based on the average of p-values from each the analyses of each imputation.

- 2) For IGA, estimates of the event rates will be based on the average of rates from each imputation. The CMH test statistic from the analysis of each imputation will be converted to a Normal Z score by taking the square root and adjusting for direction (change to a negative value if Omiganan group is worse than Vehicle). These Z scores (with SE=1) will be combined into a single p-value using PROC MIANALYZE as displayed below:

```
Proc MIANALYZE;  
Model effects estimate;  
Stderr SE;  
run;
```

Similarly, the p-values for the one-sided Fisher's Exact test of each imputation will be converted to a Normal Z score using the inverse normal function. These Z scores (with SE=1) will be combined into a single p-value using the same PROC MIANALYZE code.

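### The imputation code printed in SAP 6.2 leaves out treatment arm, so a treatment effect sustained to Week 12 is pulled part of the way towards zero

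*SAP*

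**What the plan says.** SAP 6.2 states that "All co-primary and secondary endpoints will be analyzed using MI for missing data" and that "100 imputed datasets will be generated to impute missing data using the below SAS code". The variable list is "var sex base w1 w3 w6 w9 w12" for lesions and "var sex w1 w3 w6 w9 w12" for IGA. The only CLASS variable in either call is sex. There is no BY statement, and no text in the SAP says that imputation is arm-specific.

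The completed datasets then go to the models of SAP 5.4.2. Lesion change is analysed by ANCOVA "with treatment as a main effect, and pooled center as a covariate", and the IGA endpoints by a CMH test. The lesion results "will be combined into single estimates, standard errors, and p-value using PROC MIANALYZE as displayed below". For IGA, "estimates of the event rates will be based on the average of rates from each imputation", and the CMH z-scores are pooled to one p-value.

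Two alternative treatments of missing data are planned, with limited scope: "Observed Case and Baseline Observation Carried Forward (BOCF) will be utilized for the co-primary endpoints only".

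SAP 5.4.2 and 7.0 treat every analysis as exploratory because enrolment was stopped after the interim analysis. Section 7.0 removes only the per-protocol population and the multiplicity adjustments, so MI remains primary.

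**The concern.** An imputation model should contain the variables of the analysis model, above all the one whose effect is being estimated. FCS regression uses only the VAR list. Without treatment in that list, a missing Week 12 value is predicted from the subject's earlier visits with coefficients common to both arms. Those visits carry only part of the arm difference, so vehicle dropouts are imputed somewhat too well and omiganan dropouts somewhat too badly.

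The direction depends on how the effect develops:
- sustained to Week 12: the difference is pulled part of the way to zero;
- peaks early and wanes: the Week 12 difference is overstated;
- absent at every visit: no bias, and the test is conservative.

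In an exploratory trial the estimates are the main product. At Week 12, MI and Observed Case could differ because of the code, and a reader could take that for information about the missing data. The Week 6 and Week 9 secondary endpoints have no Observed Case comparison at all.

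**Working it through.** **1. The plan's own figures.** SAP 5.1 assumes lesion reductions of 13.5 and 4 (difference 9.5), SD 12 and two-sided alpha 0.05. The t-test has power 0.948 at 42 per group and 0.952 at 43, so 43 per group reproduces. For 17% versus 6%, Fisher's exact test has power 0.951 at 225 per arm, which also reproduces. The plan gives no figure for the imputation itself.

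**2. Assumptions for the mid case.** These are not in the documents: 10 / 20 / 30% missing at Week 12; dropout unrelated to outcome, with last visit spread evenly over Weeks 1, 3, 6 and 9; correlation 0.7 between any two visits; effect building as 25/50/75/90/100% of 9.5, that is 2.375, 4.75, 7.125, 8.55 and 9.5.

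**3. Hand calculation, lesions.** With equal correlation r, the regression of Week 12 on k earlier values (baseline included, effect 0) gives each the within-arm coefficient r / (1 + (k - 1)r). The arm difference carried into the imputed value is that coefficient times the sum of the earlier effects.

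| Last visit | k | Coefficient | Sum of earlier effects | Carried |
|---|---|---|---|---|
| Week 1 | 2 | 0.7/1.7 = 0.412 | 2.375 | 0.98 |
| Week 3 | 3 | 0.7/2.4 = 0.292 | 7.125 | 2.08 |
| Week 6 | 4 | 0.7/3.1 = 0.226 | 14.25 | 3.22 |
| Week 9 | 5 | 0.7/3.8 = 0.184 | 22.8 | 4.20 |

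The mean carried is 2.62 of 9.5. With a fraction m missing, the estimate is 9.5 - m(9.5 - 2.62), or 8.81 / 8.12 / 7.44.

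The fitted regression pools the arms, so its coefficients absorb a little more of the difference. With 1:1 allocation its covariance is the within-arm matrix plus dd'/4, where d is the vector of visit effects. Solving the same four regressions with SD 12 per visit gives 1.14, 2.61, 4.23 and 5.50 carried (mean 3.37). The estimate is then 9.5 - 6.13m = 8.89 / 8.27 / 7.66. With treatment in the model the full 9.5 is carried.

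**4. Simulation with the plan's bounds and rounding.** Settings: 20 imputations, Rubin's rules, center omitted. IGA was a latent normal (autoregressive, 0.7) cut to grades 0-4, with CMH z-scores pooled as the SAP describes. Sixty per arm is the interim size; the final number is not stated. Entries are for 10 / 20 / 30% missing.

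| | 60 per arm | 225 per arm |
|---|---|---|
| Lesion difference, as printed | 8.9 / 8.3 / 7.8 | 8.8 / 8.3 / 7.7 |
| Lesion difference, BY treatment | 9.5 / 9.4 / 9.4 | 9.4 / 9.4 / 9.4 |
| Root mean squared error, as printed | 2.28 / 2.40 / 2.74 | 1.24 / 1.56 / 2.01 |
| Root mean squared error, BY | 2.30 / 2.27 / 2.44 | 1.14 / 1.14 / 1.19 |
| 95% interval coverage, as printed | 94 / 94 / 91% | 93 / 87 / 73% |
| Lesion power, as printed | 0.99 / 0.97 / 0.92 | 1.00 |
| Lesion power, BY | 0.99 / 0.99 / 0.97 | 1.00 |
| IGA 0/1 difference (points), as printed | 10.1 / 9.2 / 8.3 | 10.2 / 9.4 / 8.5 |
| IGA 0/1 difference, BY | 11.1 / 11.1 / 11.2 | 11.2 / 11.4 / 11.4 |
| IGA 0/1 difference, treatment in VAR | 10.6 / 10.3 / 9.9 | 10.8 / 10.5 / 10.1 |
| IGA rejection rate, as printed | 0.36 / 0.28 / 0.19 | 0.94 / 0.88 / 0.81 |
| IGA rejection rate, BY | 0.44 / 0.44 / 0.41 | 0.97 / 0.96 / 0.95 |

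A separately programmed simulation of the 60-per-arm lesion case gave 8.8 / 8.3 / 7.6 as printed, against 9.3-9.4 with treatment included.

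**5. Secondary lesion endpoints, 60 per arm.** As printed, Week 9 gives 8.2 / 7.7 / 7.3 against 8.5-8.6 with full data. Week 6 gives 6.9 / 6.6 / 6.4 against 7.1.

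**6. Other effect shapes.** If the effect peaks at 9.5 at Week 3 and is gone by Week 12, the printed code gives a spurious +0.4 / +0.9 / +1.3 lesions, against about 0 with BY. At 225 per arm it then rejects in 6 / 11 / 16% of trials (BY: 6 / 6 / 7%); at 60 per arm, in 5 / 5 / 6%. If the effect only falls to 5 at Week 12, the overstatement is 0.2 or less. With no effect at any visit there is no bias, and rejection is 3.9 / 3.5 / 2.9% at 60 per arm.

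**7. Range.** The large-sample calculation, over correlations of 0.3 to 0.85 and several onset curves, and allowing some dropouts to have only a baseline value, gives 8.65-9.21 at 10% missing, 7.79-8.93 at 20% and 6.94-8.64 at 30%. That is shrinkage of about 3-9%, 6-18% and 9-27%.

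**The case against.** **The benchmark assumes that dropouts keep the full benefit.** If they lose all of it, the true all-subject difference is 9.5(1 - m) = 8.55 / 7.6 / 6.65, and the printed 8.9 / 8.3 / 7.8 is closer than 9.5 / 9.4 / 9.4. At 20% missing the two options are equally far from the truth at (8.3 + 9.4)/2 = 8.85, which is a loss of (9.5 - 8.85)/(0.2 x 9.5), about one third. The arithmetic is right. But the plan states no such target, and pooling the arms does not aim at one: the pull is set by visit correlation and dropout timing, not by any assumed loss of benefit.

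**The printed code is abbreviated.** It has no DATA= or OUT=, and the single PROC MIANALYZE call shown cannot by itself give both the per-arm means and the difference. A BY line may exist in the production program. That stands: the finding concerns the plan as written, not the analysis as run.

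**The scenario is optimistic.** Enrolment stopped after a futility interim analysis, so the effect may be well below 9.5. The pull scales roughly with the effect. At a true difference of 3 (assumed) it is 3/9.5 of 0.6 / 1.2 / 1.7, about 0.2 / 0.4 / 0.5 lesions, against a standard error of about 2.3. That stands too, as do the mild results at 60 per arm with 10% missing, where total error is no worse than with BY.

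**Mitigation already in place.** Protocol 7.2.3 asks for a full evaluation at withdrawal and SAP 6.1 assigns it to a scheduled week, so many dropouts will have some post-baseline data. Observed Case does not share the pull for the co-primary endpoints.

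These points limit the consequence. None supplies a reason to leave treatment out.

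**Conclusion.** The concern holds. As written, SAP 6.2 imputes without treatment arm and then estimates a treatment effect. For a sustained effect the direction is certain: the mid case loses about 0.6 / 1.2 / 1.7 of 9.5 lesions at 10 / 20 / 30% missing with 60 per arm, and the IGA 0/1 rates move towards each other. For a fully waned effect the error goes the other way; with no effect there is none.

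The sizes rest on assumed dropout, correlation and onset, on dropout unrelated to outcome, and on dropouts keeping the effect of their arm. The 225-per-arm results describe the planned trial, not one stopped early. No confirmatory decision depends on these outputs. It should still be corrected, because MI remains the primary method and the correction is nearly free.

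**What to change.** Sort by treatment and run both PROC MI calls with a BY treatment statement. All subjects start at IGA grade 4. If IGA varies too little within an arm at early visits, add treatment to CLASS and VAR for that call instead, with a matching '.' in MIN, MAX and ROUND, because those lists are positional. State in SAP 6.2 that imputation is done within arm or conditions on arm, and fix the choice before the analysis is run. If the production program already does this, only the printed code and text need correcting.

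Limits of the fix: for lesions the two options agree to within 0.02. For IGA 0/1, against a true 11 points, BY gives 11.1-11.4 in the mid case (10.9-12.6 under wider assumptions) and treatment in VAR gives 9.9-10.8, because a bounded, rounded linear model is not exact for a 0-4 grade. Neither option adds center to the imputation model.

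Cost: one sort and one BY line per call, or one added variable and three list entries, plus one sentence. There is no data, patient or timeline cost.
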